11.4.4 Overall Objective Status

The overall objective status for an evaluation is determined by combining the patient's status on target lesions, target lymph nodes, non-target lesions, non-target lymph nodes, and new disease as defined in the following tables:

For Patients with Measurable Disease			
Target Lesions & Target Lymph Nodes	Non-target Lesions & Non-target Lymph Nodes	New Sites of Disease	Overall Objective Status
CR	CR	No	CR
CR	Non-CR/Non-PD	No	PR
PR	CR Non-CR/Non-PD	No	PR
CR/PR	Not All Evaluated*	No	PR**
SD	CR Non-CR/Non-PD Not All Evaluated*	No	SD

For Patients with Measurable Disease			
Target Lesions & Target Lymph Nodes	Non-target Lesions & Non-target Lymph Nodes	New Sites of Disease	Overall Objective Status
Not all Evaluated	CR Non-CR/Non-PD Not All Evaluated*	No	Not Evaluated (NE)
PD	Unequivocal PD CR Non-CR/Non-PD Not All Evaluated*	Yes or No	PD
CR/PR/SD/PD/Not all Evaluated	Unequivocal PD	Yes or No	PD
CR/PR/SD/PD/Not all Evaluated	CR Non-CR/Non-PD Not All Evaluated*	Yes	PD

* See [Section 11.4.3](#).

For Patients with Non-measurable Disease Only		
Non-target Lesions & Non-target Lymph Nodes	New Sites of Disease	Overall Objective Status
CR	No	CR
Non-CR/Non-PD	No	Non-CR/Non-PD
Not All Evaluated*	No	Not Evaluated (NE)
Unequivocal PD	Yes or No	PD
Any	Yes	PD

* See [Section 11.4.3](#).

11.4.5 Symptomatic Deterioration: Patients with global deterioration of health status requiring discontinuation of treatment without objective evidence of disease progression at that time, and not either related to study treatment or other medical conditions, should be reported as PD due to “symptomatic deterioration.” Every effort should be made to document the objective progression even after discontinuation of treatment due to symptomatic deterioration.

11.5 Definitions of Analysis Variables

Formal definitions of variables used in analyses can be found in the Statistical Considerations section of the protocol.

11.6 Surgical Pathologic Determination of Treatment Response

Pathologic response to neoadjuvant therapy will be documented at the site by using the information from the local operative report and local pathology report. This will be utilized at the site for individual patient care, and the information will also be included in the statistical analysis in the secondary endpoint of R0 resection. See [Section 11.7](#) for further information.

In addition, there will be a retrospective central pathology review that documents the pathologic response to neoadjuvant therapy that will be included in the statistical analysis, but will NOT be utilized for the management of the individual patient.

Histopathologic response to preoperative therapy will be determined by analysis of the resected surgical specimen by the pathologist (see [Section 7.3](#)). The following grades will be used to semi-quantitatively characterize treatment response:

- I - 0% residual tumor cells in the specimen (pCR)
- II - 1 to < 5% residual tumor cells in the specimen
- III - \geq 5% residual tumor cells in the specimen

11.7 Histopathologic Determination of R-status

11.7.1 “Macroscopic disease” is assessed by surgeon and “microscopic disease” is assessed by the histopathologist.

11.7.2 Margins to be assessed in this trial include: 1) common bile duct, 2) SMA margin, 3) pancreatic neck as described in pathology section:

- R0- Macroscopically complete tumor removal with negative microscopic surgical margins.
- R1- Macroscopically complete tumor removal with positive microscopic margins (any or all).
- R2- Macroscopically incomplete tumor removal with known or suspected residual gross disease.

11.8 Treatment Evaluation after Completion of Surgery and Post-operative Chemotherapy

11.8.1 The term “recurrence” is used if cancer returns either in the locoregional area of the primary tumor or at distant sites following R0 or R1 resection.

11.8.2 Recurrence is determined radiographically and biopsy need not be performed except as detailed below or when CT findings are equivocal in the determination of the enrolling physician.

Locoregional Recurrence: identified by a new soft-tissue mass around the mesenteric vasculature or regional lymph nodes. Note that soft-tissue in this location on early postoperative scans may be benign and due to postoperative changes. Such findings may be difficult to distinguish from early tumor progression. In cases in which the diagnosis is ambiguous, discussion with the PI should occur. Performance of tissue biopsy should be considered prior to assigning a diagnosis of locoregional recurrent disease.

Distant Recurrence: identified by a new hypodensity in the liver or nodule(s) in the lungs or peritoneum. Other sites of presumptive distant recurrence (adrenal, brain) should require prompt biopsy confirmation. New ascites should be interrogated with aspiration and cytology if it is an isolated finding and should not necessarily be taken to indicate carcinomatosis, particularly following the performance of resection and reconstruction of the mesenteric vein(s).

12.0 END OF TREATMENT/INTERVENTION

12.1 Duration of Treatment

12.1.1 CR, PR, or SD: Patients who are in CR, PR or SD will continue on therapy until disease progression (see [Section 12.1.3](#)), excess toxicity or patient withdrawal.

After treatment is discontinued, patients will be followed per the Study Calendar in [Section 5.0](#).

12.1.2 Disease Progression

Remove from protocol therapy any patient with disease progression as per [Section 12.1.3](#) or recurrence after surgery (either Arm 1 or Arm 2 patients). Document details, including tumor measurements, on data forms.

After disease progression, patients should be followed for survival per the study calendar ([Section 5.0](#)).

Note: Biochemical progression (B-PROG) without the demonstration of objective progression (PD) of target or non-target lesion will not be sufficient indication to remove the patient from the study (see [Section 11.4.3](#)).

12.1.3 Removal of Patients from Protocol Therapy:

In the absence of treatment delays due to adverse events, treatment will be completed unless the patient experiences any one of the following scenarios. The specific indication should be described as:

- Metastatic disease identified on imaging studies
- For patients with RECIST PD with local progression only, the treating investigator should decide whether continuing protocol treatment is in the best interest of the patient
- The presence of locally advanced disease on pre-surgical restaging imaging studies (see [Appendix II](#) for definition of locally advanced pancreatic cancer)
- Decline in PS in the absence of radiographic evidence for disease progression if PS cannot be recovered (symptomatic deterioration)
- Metastatic disease identified intraoperatively and biopsy-proven
- Unresectable disease identified intraoperatively (e.g., locally infiltrative disease without metastases for which the surgeon does not feel resection is safe)
- R2 surgical resection
- Nontherapeutic (aborted) operation for any other reason
- Intercurrent illness that prevents further administration of treatment
- Unacceptable adverse event(s)
- Patient decides to withdraw from the study
- General or specific changes in the patient's condition that render the patient unacceptable for further treatment in the judgment of the investigator

Patient should be removed from protocol therapy, and followed as per [Section 5.0](#), post-treatment follow-up. Protocol treatment will be discontinued and further treatment is at the discretion of the treating physician.

12.1.4 Follow-up for Patients Removed from Protocol Therapy:

For patients who are removed from protocol therapy in any instance listed in [Section 12.1.3](#), follow patients per the schedule found in [Section 5.0](#) of the protocol for clinical and survival status.

12.2 Managing Ineligible Patients and Registered Patients Who Never Receive Protocol Intervention

12.2.1 Definition of Ineligible Patient

A study participant who is registered to the trial but does not meet all of the eligibility criteria is deemed to be ineligible.

12.2.2 Follow-up for Ineligible Patients Who Continue with Protocol Treatment

Patients who are deemed ineligible after registering may continue protocol treatment, provided the treating physician, study chair, and executive officer agree there are no safety concerns if the patient continues protocol treatment. All scans, tests, and data submission are to continue as if the patient were eligible. Notification of the local IRB may be necessary per local IRB policies.

12.2.3 Follow-up for Ineligible Patients Who Discontinue Protocol Treatment

For patients who are deemed ineligible after registering to the trial, who start treatment, but then discontinue study treatment, the same data submission requirements are to be followed as for those patients who are eligible and who discontinue study treatment.

12.2.4 Follow-up for Patients Who Are Registered, but Who Never Start Protocol Treatment

For all study participants who are registered to the trial but who never receive study intervention (regardless of eligibility), the follow-up requirements are specified below.

Baseline, off treatment, and post-treatment follow up (i.e. relapse, progression, and survival) data submission is required. See the Data Submission Schedule accompanying the All Forms Packet.

12.3 Extraordinary Medical Circumstances

If, at any time the constraints of this protocol are detrimental to the patient's health and/or the patient no longer wishes to continue protocol therapy, protocol therapy shall be discontinued. In this event:

- Document the reason(s) for discontinuation of therapy on data forms.
- Follow the patient for protocol endpoints as required by the Study Calendar.

13.0 STATISTICAL CONSIDERATIONS

Note: Arm 2 closed to new patient enrollment on 08/13/2018.

13.1 Study Endpoints

13.1.1 Primary Endpoint

The primary endpoint of this study is the 18-month OS rate, defined as the number of patients who are alive at 18 months after randomization divided by the total number of evaluable patients in each arm. An evaluable patient is defined as any patient who signed informed consent, deemed eligible by central review and received any protocol-defined treatment.

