13.2 Sample Size

We anticipate enrolling a maximum of 124 evaluable patients (62 per arm) per statistical design. Additional 10 (5 per arm) patients will be accrued to account for cancelations, ineligibilities, major violations, and lost-to-follow up, etc. Thus the total targeted accrual will be 134 patients.

We anticipate to pre-register 5 patients per month. Since we estimate 80% of patients who are pre-registered for central review will be randomized to therapy, the actual accrual will be 4 patients per month. Thus, we expect to pre-register 168 patients to reach the targeted accrual of 134 patients. The accrual period of this study is estimated to be 34 months.

We also expect that 40% of patients randomized to therapy will be off protocol treatment prior to surgery (i.e. will not undergo surgery). Therefore we expect that of the 134 patients, 80 will proceed to surgery. The primary endpoint, overall survival at 18 month post randomization, is well-defined even among patients who do not receive surgery. Therefore, the percentages of patients who do not undergo surgery do not affect the trial design.

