13.4.1.2 Final Analysis

The primary efficacy analysis will be performed on 18-month OS rate for the two treatment arms, separately, based on all evaluable patients. For each given treatment arm, if full accrual is reached and at least 36 patients (i.e. ≥ 36 patients) out of 62 evaluable patients are alive up to 18 months after randomization, the regimen of the evaluated arm will be considered worthy of further testing in this disease population. Otherwise, the regimen will be deemed inefficacious. The final analysis will be carried out approximately 18 months after the last patient, in each arm, is enrolled. This will occur approximately 52 months after trial activation.

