13.4.1.3 Analysis Plan

The treatment arm specific 18 month OS rate and 95% confidence interval will be estimated based on standard method [39]. Chi-squared test (or Fisher's exact test if the data in contingency table is sparse) will be used to compare 18 month OS rates among treatment arms. Overall survival within each arm will be summarized by Kaplan-Meier method. Median, 1-year and 2-year rates will be estimated based on Kaplan-Meier curves.

If both arms are deemed worthy of further testing in this disease population, a log-rank test will be used to compare the median OS between the two arms. A "pick-the-winner" approach will be utilized, meaning that the nominally better arm (the arm with higher 18-month OS rate, by any amount) will be prioritized for future study.

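### The primary 18-month OS count has no rule for treated patients lost to follow-up; read literally it can never count them as alive, although Section 13.2 treats them as covered by extra accrual

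*Combined protocol and SAP*

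**What the plan says.** **Endpoint.** Section 13.1.1 takes the "number of patients who are alive at 18 months after randomization divided by the total number of evaluable patients in each arm". On who is evaluable: "An evaluable patient is defined as any patient who signed informed consent, deemed eligible by central review and received any protocol-defined treatment".

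**Decision.** Section 13.4.1.2: "The primary efficacy analysis will be performed on 18-month OS rate for the two treatment arms, separately, based on all evaluable patients". An arm that reaches full accrual is carried forward if at least 36 "out of 62 evaluable patients are alive up to 18 months after randomization".

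**Sample size.** Section 13.2: "We anticipate enrolling a maximum of 124 evaluable patients (62 per arm) per statistical design", and then "Additional 10 (5 per arm) patients will be accrued to account for cancelations, ineligibilities, major violations, and lost-to-follow up, etc".

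**Power.** Section 13.3 states 82% power per arm for an 18-month rate of 63% against 50%, at one-sided 0.07.

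**Kaplan-Meier.** Section 13.4.1.3 uses it to summarize OS: "Median, 1-year and 2-year rates will be estimated based on Kaplan-Meier curves". The primary 18-month rate and its interval follow a binomial method for multistage tests (reference 39).

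No section says what happens to a patient whose status at 18 months is unknown, and none gives an expected loss rate.

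**The concern.** The two sections disagree about a patient who starts treatment and later disappears. Cancellation before treatment or central ineligibility takes a patient out of the evaluable set, so the extra accrual can replace that patient. Loss after treatment does not. The patient remains in the denominator and has no route into the numerator, so for the 36-of-62 rule the effect is the same as a death.

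What is at stake is the only efficacy decision for the arm. Each such loss pulls the estimate down and makes it likelier that an effective regimen is declared inefficacious for administrative reasons. The primary 18-month figure could also differ from the Kaplan-Meier curve reported beside it.

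**Working it through.** **Inputs.** n = 62 and cut-off 36 (13.4.1.2); rates 0.50 and 0.63, stated power 82% and one-sided 0.07 (13.3); futility stop at 11 or fewer R0 resections in 30 (13.4.1.1), with stopping probabilities of 43% and 0.8% (13.3).

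**1. Reproducing the plan's figures.** Exact binomial:

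- P(X ≥ 36 | 62, 0.63) = 0.826 and P(X ≥ 36 | 62, 0.50) = 0.126.
- P(X ≤ 11 | 30, 0.60) = 0.0083 and P(X ≤ 11 | 30, 0.40) = 0.431, matching the stated 0.8% and 43%.
- Taking R0 and OS as independent, power = 0.826 × (1 − 0.0083) = 0.819 and error = 0.126 × (1 − 0.431) = 0.072. These match 82% and 0.07.

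The 82% is therefore the power when all 62 outcomes are known.

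**2. Literal count with losses.** Let k of the 62 have a loss time before 18 months, unrelated to survival. They cannot be counted alive, so power = P(X ≥ 36 | 62 − k, 0.63), multiplied by 0.9917 for the interim. The expected rate is 0.63 × (62 − k)/62. The range of k is assumed.

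| k | Expected rate if truth is 63% | Power before interim | Power with interim | Error at 50%, before interim |
|---|---|---|---|---|
| 0 | 63.0% | 82.6% | 81.9% | 12.6% |
| 1 | 62.0% | 78.3% | 77.6% | 10.0% |
| 2 | 61.0% | 73.3% | 72.7% | 7.8% |
| 3 | 60.0% | 67.7% | 67.1% | 5.9% |
| 5 | 57.9% | 54.9% | 54.5% | 3.1% |

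**3. Could the extra five absorb the losses?** Only under a rule that the plan does not give. Suppose all 67 in an arm are evaluable and five are lost. A proportional cut-off (67 × 36/62 = 38.9, so 39) gives 56.3% power. Keeping 36 gives 82.6%, but that rule has a 31% false-positive rate if nobody is lost. All three figures are before the interim.

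**4. Kaplan-Meier at 18 months, same 62 patients.** Simulation of 40,000 trials per setting: exponential survival, k patients assigned a loss time uniform on 0 to 18 months, arm passes if the estimate is at least 36/62. The mean estimate stays at the true rate. For k = 1 to 5, power is about 78-79% and error at 50% is 0.10-0.11, both before the interim. The like-for-like comparison is with the before-interim power column in step 2:

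- k = 1: 78.3% for the count, about 78.5% for Kaplan-Meier, so almost no gain.
- k = 2: 73.3% against 78-79%.
- k = 3: 67.7% against 78-79%.

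The gain at one loss is negligible because 35/61 = 0.574 is below 36/62 = 0.5806. In nearly all cases 36 of the other 61 must still be alive.

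**5. The exact cut-off matters.** 36/62 = 0.58065, which is below 0.581. A cut-off written as 58.1% would fail an arm with 36 of 62 alive and in effect require 37. With no losses, P(X ≥ 37 | 62, 0.63) = 0.751.

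**The case against.** The strongest reply is that the plan nowhere says lost patients count as not alive. Section 13.2 points the other way: if lost patients are replaced until 62 have known status, the 82% stands. This is right as far as it goes; the scoring is a consequence of the literal definition and not a stated imputation rule. But replacement contradicts Section 13.1.1, which keeps a treated patient evaluable whatever happens later, and Section 13.4.1.2, which analyses all evaluable patients.

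Second, losses may be few. Survival status is required every 6 months for 5 years, also after removal from treatment (Sections 5.0 and 12.1.4), and the final analysis comes about 18 months after the last enrolment. This stands. Five treated patients lost would use the whole allowance for an arm, which must also cover cancellations, ineligibility and violations. A reader might infer from the last row of the table that the trial has 54% power; with no loss rate in the documents, that is not supported.

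Third, the literal count is conservative: its error falls along with its power. This also stands. Part of the Kaplan-Meier advantage comes from accepting an error of 0.10-0.11 where the count would have 0.08 or less with two or more losses. That is still below the no-loss 0.126.

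Fourth, the design is explicitly exact binomial (Section 1.2), so a Kaplan-Meier decision reaches into the interval method. That is a real cost. The planned Kaplan-Meier summary of OS lets a reader see an 18-month value, but it does not drive the decision.

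**Conclusion.** The concern holds in limited form. Sections 13.1.1 and 13.2 do not agree on treated patients who are lost, and no rule covers unknown 18-month status. Applied literally, the primary rate is biased downward. Power including the interim falls from 81.9% to 77.6%, 72.7% and 67.1% with one, two and three losses, that is, by about 4 to 6 points for each.

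This assumes that losses are unrelated to survival, that R0 and OS are independent in the interim factor, and that one to three losses is a reasonable range.

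Two further inferences should be resisted. The false-positive rate is not inflated by losses; it falls. Kaplan-Meier does not restore 82%; it removes the bias and holds power near 78-79% before the interim. The issue bears on an arm that reaches full accrual. Since Arm 2 closed to enrolment on 08/13/2018, that means Arm 1.

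**What to change.** Before the final analysis, amend Sections 13.1.1, 13.4.1.2 and 13.4.1.3 as follows:

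- Estimate the 18-month OS rate by Kaplan-Meier in all evaluable patients, and declare the arm promising if the estimate is at least 36/62 exactly (0.5806), not a rounded 58.1%. With no losses this is identical to the present rule.
- Report the count with lost patients as not alive as a sensitivity analysis.
- Reconcile Section 13.2 with Section 13.1.1. Either drop loss to follow-up from what the extra accrual is said to cover, or, if replacement was intended, require known 18-month status in the definition of evaluable and give the cut-off for any number other than 62.
- Choose a confidence interval that matches the Kaplan-Meier estimate.

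The cost is wording and restated operating characteristics; no new patients or data are needed. The downsides are an assumption of non-informative censoring, a higher error rate than under the conservative count, and almost no benefit if only one patient is lost.

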13.3 Power Justification

The primary aim of this randomized phase II study is to evaluate 18-month OS rate in patients with borderline resectable cancer of the head of the pancreas treated neoadjuvantly using one of the following regimens: 1) Arm 1: 8 cycles of systemic FOLFIRINOX or 2) Arm 2: 7 cycles - of systemic FOLFIRINOX followed by short-course hypofractionated radiation therapy. All patients who are able to undergo subsequent surgery will also receive 4 cycles of postoperative FOLFOX. Eligible patients will be randomized and stratified by ECOG performance score onto two arms. Within each arm, single-arm sequential design with one interim analysis for futility will be implemented. The final efficacy analysis and interim analysis will be based on 18-month OS rate and R0 resection rate, respectively, and evaluated in each arm separately. The comparison of OS between arms will be carried out only if both arms are deemed promising at the end of the trial. “Pick-a-winner” strategy will be implemented to choose one treatment strategy for recommendation.

An extensive literature review was conducted to evaluate median OS and R0 resection rate in patients purported to have “borderline resectable” tumors who received chemo, chemoRT, etc. were conducted. Twenty-six studies published between 2004 and 2015 are identified with number of borderline resectable patients range from 8 to 129. All but three of these studies are retrospective studies.

The following table summarizes the historical data of median OS and R0 resection rate among all patients started treatment, including both patients with and without surgery.

Time era	Among Studies with N > 20				Among Studies with N > 50			
	N of studies	Weighted	Median	Range (IQR)	N of studies	Weighted	Median	Range (IQR)
Median OS in months								
Prior to 2012	6	21.3	21.5	14.2 – 25 (18.0 – 22.8)	3	22.0	22.0	14.2 – 25 (21.5 – 22.5)
2012 and later	9	21.2	19.9	17.2 – 28 (18.0 – 23.6)	6	21.2	21.0	17.2 – 28 (17.9 – 23.2)
All studies	15	21.2	21.0	14.2 – 28 (17.6 – 23.3)	9	21.5	22.0	15 – 28 (19.0 – 23.0)
R0 Resection Rate Among All Patients Started Neoadjuvant Treatment								
Prior to 2012	6	41.4%	36.9%	30 – 59%	3	43.0%	38.8%	30 – 59%
2012 and later	9	61.2%	54.4%	42 – 92%	6	60.0%	54.2%	42 – 92%
All studies	15	53.0%	53.4%	30 – 92%	9	52.8%	53.9%	37 – 92%

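### The between-arm efficacy comparisons leave out randomized patients who never start treatment, although their survival is collected; the effect is probably small and cheap to remove

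*Combined protocol and SAP*

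**What the plan says.** Section 13.1.1 defines the primary endpoint as the number alive 18 months after randomization "divided by the total number of evaluable patients in each arm", and adds: "An evaluable patient is defined as any patient who signed informed consent, deemed eligible by central review and received any protocol-defined treatment". Section 13.4.1.2 runs the final efficacy analysis for each arm "based on all evaluable patients", with success at 36 or more alive out of 62.

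Section 13.4.1.3 then says that a chi-squared or Fisher test "will be used to compare 18 month OS rates among treatment arms". If both arms succeed, the winner is "the arm with higher 18-month OS rate, by any amount". Section 13.3 limits when this happens: "The comparison of OS between arms will be carried out only if both arms are deemed promising at the end of the trial".

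Sections 13.1.2.1 and 13.1.2.3 define two cohorts each for R0 and pCR. One requires protocol treatment and the other requires surgery. Sections 13.4.2.2 and 13.4.2.3 compare both rates between arms, with no condition that both arms be promising.

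For registered patients who never start, Section 12.2.4 says: "Baseline, off treatment, and post-treatment follow up (i.e. relapse, progression, and survival) data submission is required". No analysis of overall survival in all randomized patients is planned, not even as a sensitivity analysis.

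**The concern.** The clock starts at randomization, but entry to the denominator depends on something that happens later. Section 7.0 has treatment begin within 14 days of registration. A patient who dies, deteriorates or withdraws in that window drops out of the endpoint. For a single-arm test against a historical rate this is a usual choice. For a comparison of randomized arms it gives up part of the protection that randomization offers. The arms cannot be masked, because one includes radiotherapy, so the decision to start may depend on the assignment. An arm that loses more patients with poor prognosis before treatment looks better in the treated set than it is over all patients assigned to it.

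Two uses are affected. A winner chosen on any margin, however small, can be decided by one patient. Section 1.3 also says that if only one arm is clinically relevant, it becomes the control arm for future randomized trials. Those trials need to know the rate among everyone assigned, or at least how far it lies from the treated-set rate.

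**Working it through.** **Which condition removes randomized patients.** The definition has three parts: consent, central eligibility and receipt of treatment. Sections 4.4 and 7.4.2 put central review before registration and randomization, and consent comes earlier still. Receipt of treatment is the part settled after randomization.

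**Inputs from the protocol.**
- 62 evaluable patients per arm, and 5 extra per arm for cancellations, ineligibility, major violations and loss to follow-up (Section 13.2).
- 18-month OS of 50% under the null and 63% under the alternative; one-sided level 0.07; power 82%; interim stopping probabilities 43% and 0.8% (Section 13.3).
- Interim stop at 11 or fewer R0 resections in 30 (Section 13.4.1.1); success at 36 or more of 62 (Section 13.4.1.2).

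**Assumptions.** The protocol gives neither the number of never-starters nor their survival. I take 0 to 5 per arm, and 18-month OS s of 20% to 40%.

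**The plan's own figures, by exact binomial.**
- Interim stop: P(X ≤ 11 | 30, 0.40) = 0.431 and P(X ≤ 11 | 30, 0.60) = 0.008.
- Final rule alone: P(X ≥ 36 | 62, 0.50) = 0.126 and P(X ≥ 36 | 62, 0.63) = 0.826.
- Combined, with R0 independent of survival: 0.569 × 0.1264 = 0.072 and 0.992 × 0.8258 = 0.819.

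The stated 0.07, 82%, 43% and 0.8% reproduce, and they belong to 62 treated patients. Moving the rule to 67 would need a new cutoff. With 39 of 67, the same steps give 0.569 × 0.1108 = 0.063 and 0.992 × 0.8264 = 0.820 if never-starters survive like the others. Power falls to about 0.67 if only 25% of them do (0.992 × 0.6765).

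**Per-arm rate with all 5 extra patients as never-starters.** Formula: (62 × 0.63 + 5s) / 67.
- s = 0.20: (39.06 + 1.0) / 67 = 59.8%.
- s = 0.40: (39.06 + 2.0) / 67 = 61.3%.

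The treated-set rate is 63% in both cases.

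**Between-arm difference, both arms at 63% among starters.** With a never-starters in one arm and 5 in the other, the all-randomized difference is (39.06 + a·s) / (62 + a) − (39.06 + 5s) / 67.

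| Never-starters | s = 20% | s = 30% | s = 40% |
|---|---|---|---|
| 0 vs 5 | 3.2 points | 2.5 points | 1.7 points |
| 2 vs 5 | 1.9 points | 1.4 points | 1.0 point |

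The treated-set comparison shows no difference in any of these cells. With a 2 vs 3 split the shift is at most 0.9 points, even if no never-starter survives: 39.06/64 − 39.06/65 = 0.9 points.

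**Scale.** One patient in 62 is 1.6 points, so the range of 1.0 to 3.2 points is roughly one or two patients. The standard error of the difference between two arms of 62 at 63% is √(2 × 0.63 × 0.37 / 62) = 8.7 points.

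**The case against.** The case against giving this much weight is substantial, and most of it stands.

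- **The comparison may never be made.** Section 13.3 makes the OS comparison conditional on both arms being promising, and Section 13.4.1.2 also requires full accrual. Section 7.0 closed Arm 2 to enrollment, and stopped its treatment, on 08/13/2018. If Arm 2 was then short of 62 evaluable patients, no winner is picked; its count is not given. This limits the point but does not remove it. The chi-squared sentence in Section 13.4.1.3 carries no such condition, the R0 and pCR tests are unconditional, and the per-arm rate is reported in any case.
- **Non-starting should differ little between arms.** Both arms open with the same mFOLFIRINOX and differ only after cycle 7. A 0 vs 5 split is an extreme case. One route to imbalance does appear in the text: a patient assigned to Arm 2 shortly before closure, and not yet treated, may be lost because of the assignment. The 14-day window suggests that such patients are few.
- **The 5 spare patients cover other losses too,** so 5 never-starters per arm is an upper bound.
- **The treated set matches the benchmark.** Section 13.3 describes its historical data as coming from patients who started treatment. This is why the 36-of-62 rule should stay as it is.

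Three stronger readings are tempting and are not supported. A reader might infer that patients are not analyzed in their assigned arm, but nothing in the plan moves a patient between arms. A reader might infer that the primary per-arm decision is invalid, but its set fits its benchmark and its operating characteristics reproduce. A reader might infer that every between-arm test drops never-starters. For the log-rank test of OS (Section 13.4.1.3) and for event-free survival (Sections 13.1.2.2 and 13.4.2.1), however, no population is stated.

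**Conclusion.** The point holds in a limited form. The treated-set denominator is carried from a single-arm decision, where it belongs, into between-arm comparisons, where all randomized patients would be less open to bias. Missing data do not force this, since Section 12.2.4 requires survival on never-starters.

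The size is modest: 63% against 59.8-61.3% for one arm, and about 1.0-3.2 points between arms. These figures rest on the upper bound of 5 never-starters in an arm and on assumed survival of 20-40%; a more even split gives less. Shifts of this size are well within sampling error and would rarely change a test result. They could change which arm is named the winner, because that rule has no margin. The populations for the log-rank and event-free survival tests are a gap in the text to be filled.

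**What to change.** 1. Leave the treated set in place for the 36-of-62 rule and for the adverse-event comparison in Section 13.4.2.4, where untreated patients would only dilute toxicity rates.
2. In Sections 13.4.1.3 and 13.4.2.1 to 13.4.2.3, state that any between-arm efficacy comparison uses all patients randomized while both arms were open, by assigned arm. This covers 18-month OS, the choice of winner, log-rank OS, event-free survival, and R0 and pCR on the all-patient denominator. Arm 1 patients enrolled after Arm 2 closed have no concurrent comparator and stay out of these comparisons.
3. For each arm, report the number of never-starters and the 18-month OS rate in all randomized or registered patients beside the treated-set rate.
4. State how a never-starter is counted for R0 and pCR, and how one lost to follow-up before 18 months is handled.

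The cost is a change of SAP wording and one extra set of tables. No further accrual or data collection is needed, and the primary decision rule does not change. The reported all-randomized rates will probably be slightly lower than the treated-set rates.
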